### 9.3. ADVERSE EVENTS

AEs will be coded using MedDRA v11.1.

AEs will be considered MTT-emergent if they started within 2 days after MTT (MTT day and the day after) but before Treatment Day 1.

AEs will be considered treatment-emergent unless there is clear indication that the event occurred prior to Treatment Day 1 (i.e. AEs starting on Treatment Day 1 will be assumed to have occurred after the first dose of trial medication) or the start date is >28 days after permanent discontinuation of trial medication. MEAEs cannot be treatment-emergent AEs (TEAEs) unless they worsen on or after Treatment Day 1. AEs present prior to Treatment Day 1 that increased in intensity or relationship to trial medication while the subject was on trial medication or within 28 days of permanent discontinuation from trial medication will be classed as TEAE. Events with missing or partial dates will be handled such that in the absence of contradictory information an AE is treatment-emergent. So for a missing start date (where stop date is after date of Treatment Day 1) the date will be imputed as the date of Treatment Day 1; for a missing stop date the date will be imputed as the date of last participation in the trial. If a partial date is recorded, the following convention will be used to assign the AE:

- If a partial date is missing a start day and month/year is the same as the date of Treatment Day 1 then use the date of Treatment Day 1, else '01' will be used for the day; if a start date is missing a month and the year is the same as the date of Treatment Day 1 then use the date of Treatment Day 1, else January will be used for the start month.
- If a partial date is missing a stop day and month/year is same as last participation date then use last participation date, else last day of the given month will be used for the stop day; if a stop date is missing a month and year is the same as last participation date then use last participation date, else December will be used for the stop month.

AEs will be summarized by SOC and PT. Subjects will be counted once at the SOC level and once at each PT within the SOC level. Where applicable, summaries will include number and percentage of subjects who report at least one AE, number and percentage of subjects reporting at least one AE in a SOC, number and percentage of subjects reporting at least one AE in a PT, and total number of events within a SOC and within a

Pharmaxis Ltd

DPM-CF-303

Final v1.0

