1.1.5 Safety

Detailed description on the safety of inhaled dry powder mannitol in subjects with cystic fibrosis can be found in the *Investigator's Brochure*, section SAFETY IN BRONCHITOL CLINICAL TRIALS.

A total of 672 subjects have received mannitol in all the completed mannitol CF studies. The most frequently reported adverse drug reactions (ADRs) were cough (9.23 %), condition aggravated (cystic fibrosis pulmonary exacerbation) (6.10 %) and hemoptysis (5.36 %). Cough was very common (> 1/10), condition aggravated and hemoptysis were common (frequency ≥ 1/100, < 1/10).

Other common ADRs (frequency ≥ 1/100, < 1/10) were: pharyngolaryngeal pain, headache, wheezing, bronchospasm, productive cough, throat irritation, post-tussive vomiting and vomiting, chest discomfort, upper and lower respiratory tract infections, and bacteria identified in the sputum.

Adverse events with a difference of at least 2 % between mannitol 400 mg b.i.d. and control in the combined Phase 3 data (DPM-CF-301 and DPM-CF-302) are listed in Table 3.

Table 3: Adverse events with a difference of at least 2 % between mannitol 400 mg b.i.d. and control in the combined Phase 3 data (DPM-CF-301 and DPM-CF-302)

MedDRA System Organ Class/ Preferred Term	Mannitol 400 mg b.i.d. N=361 n (%)	Control N=239 n (%)
Gastrointestinal Disorders		
Diarrhea	17 (4.7)	6 (2.5)
Vomiting	22 (6.1)	6 (2.5)
General Disorders and Administration Site Conditions		
Condition aggravated	133 (36.8)	96 (40.2)
Infections and Infestations		
Lower respiratory tract infection	22 (6.1)	24 (10.0)
Nervous System Disorders		
Headache	64 (17.7)	50 (20.9)
Reproductive System and Breast Disorders		
Dysmenorrhea	8 (2.2)	0 (0.0)
Respiratory, Thoracic and Mediastinal Disorders		
Cough	76 (21.1)	40 (16.7)
Hemoptysis	34 (9.4)	13 (5.4)
Pharyngolaryngeal pain	44 (12.2)	18 (7.5)

Post-hoc analysis of CF-301 and CF-302 studies found that the incidence of hemoptysis was similar in the mannitol 400 mg and control arms of these studies in adults, although this has not been tested prospectively.

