#### For Safety data:

- On-treatment period: period of time while the subject is on trial medication; it starts with the first intake of trial medication after randomization and ends 28 days after the last trial medication intake.

All safety analyses will be conducted considering the measurements and AEs observed during the on-treatment period (excluding MTT-emergent AEs [MEAEs]).

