## Statistical Analysis Plan

Imputation of missing FEV1 measurements by means of BOCF is a reasonable assumption in studies of adult subjects with cystic fibrosis, as those subjects who discontinue will no longer receive treatment and are thus likely to promptly return to their baseline lung function. Imputation by BOCF specifically inhibits any possible prolongation of an observed early treatment benefit implicitly conferred by a mixed model. Considering the higher drop-out rate observed with the experimental treatment compared to control in previous studies (DPM-CF-301 and DPM-CF-302), BOCF is not likely to favour the mannitol arm.

The primary analysis will target the de facto estimand assessing the effect of a treatment policy (Estimand 1 in Mallinckrodt ) by:

- Including all available on-treatment and off-treatment period data.
- Handling missing data based on a clinically reasonable assumption not biased in favor of the mannitol arm.

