## Statistical Analysis Plan

PT. Tables will be sorted by decreasing frequency (overall) of SOC, and then, within a SOC, descending frequency (overall) of PT.

Trial medication related AEs are defined as those that are ‘possibly related’, ‘probably related’, or ‘definitely related’. Relationship to trial medication is not expected to be missing after data cleaning, however, if relationship is confirmed as missing, the AE will be considered as related.

An overall summary table of TEAEs will be presented detailing the number and percentage of subjects, and number of events for the following categories:

- At least one TEAE.
- TEAEs related to trial medication.
- Serious TEAEs.
- Related serious TEAEs.
- TEAEs leading to permanent discontinuation of trial medication.
- TEAEs leading to withdrawal from the trial.
- TEAEs leading to death.

[figure not shown]
The incidence of all TEAE by SOC and PT will be presented for the following:

- All TEAEs.
- TEAEs related to trial medication.
- Serious TEAEs.
- Related serious TEAEs.
- TEAEs leading to permanent discontinuation of trial medication.
- TEAEs leading to withdrawal from the trial.

In addition, a summary of all TEAEs by maximum intensity (mild, moderate, severe), SOC, and PT will be presented, where the maximum intensity per subject will be counted at each level of summarization. AEs leading to death (all AEs with outcome recorded as ‘Fatal’ on the CRF), serious AEs (all AEs marked as serious on the CRF), and AEs Leading to withdrawal from the trial (all AEs with ‘Did the subject withdraw from the study due to this event?’ recorded as ‘Yes’ on the CRF) will be listed separately.

MEAEs will be summarized by SOC and PT for the MTT set.

[figure not shown]
Additional information has been collected for AEs that are considered to be hemoptysis events in this trial i.e. information on infection, hemoptysis volume, and whether the hemoptysis occurred concurrently with an exacerbation. These data will be listed and summarized separately.

Pharmaxis Ltd

DPM-CF-303

Final v1.0

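### Treatment-emergent AEs, including hemoptysis, are reported as crude percentages and counts with no allowance for time at risk; if more subjects stop drug early on mannitol, its relative risk may be modestly understated.

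*SAP*

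**What the plan says.** - **Measure.** SAP 9.3 gives subject numbers and percentages by SOC and PT: "Subjects will be counted once at the SOC level and once at each PT within the SOC level". Event totals stand beside them: "An overall summary table of TEAEs will be presented detailing the number and percentage of subjects, and number of events". SAP 6.1 makes the percentage denominator a count of subjects.
- **Window.** SAP 6.2.7 defines the safety on-treatment period: "it starts with the first intake of trial medication after randomization and ends 28 days after the last trial medication intake". It adds: "All safety analyses will be conducted considering the measurements and AEs observed during the on-treatment period". SAP 9.3 matches this, since an AE is not treatment-emergent if "the start date is >28 days after permanent discontinuation of trial medication".
- **Follow-up.** Protocol 9.2 keeps subjects who stop drug in the trial, so their later AEs are collected but fall outside these tables. Protocol 8.3.4.1 ends AE reporting 7 days after the last visit.
- **Drop-out.** SAP 8.1.1 argues that BOCF will not favor mannitol: "Considering the higher drop-out rate observed with the experimental treatment compared to control in previous studies". SAP 8.1.2 repeats the argument for the responder analysis. Neither gives a percentage.
- **Hemoptysis.** Protocol 8.3.3.1 names it as of special interest. Protocol 1.1.5 reports 34/361 (9.4%) on mannitol and 13/239 (5.4%) on control in the combined earlier trials. It then says incidence was similar between arms in adults in a post-hoc analysis, "although this has not been tested prospectively". SAP 9.3 promises a separate listing and summary, with no form stated.
- **Inference.** SAP 9 plans no inferential testing of safety data.

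**The concern.** A subject who stops drug at Week 4 can contribute events for about 8 weeks. A completer contributes about 27 weeks. Both count as one in the denominator. If early stopping is commoner on mannitol, the two percentages rest on different amounts of observation, and the shortfall falls on the mannitol side. Event totals do not repair this, because a count from shorter windows is also lower.

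The premise is one the sponsor itself uses. Higher drop-out on mannitol is cited where it makes the efficacy analysis conservative, but is not carried into Section 9, where it would act in mannitol's favor. The tools are already in the SAP: person-year rates and a log follow-up offset for exacerbations (4.2.1, 8.2.5), and Kaplan-Meier curves for withdrawal and for stopping drug (7.1.2, 7.1.3).

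At stake is the hemoptysis question. Protocol 1.2 says the trial is to give prospective safety evidence in adults. A bare pair of percentages carries neither time at risk nor uncertainty.

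**Working it through.** **1. The documents' own figures.** 34/361 = 9.4% and 13/239 = 5.4%; both reproduce. Using the rounded percentages, the ratio is 9.4/5.4 = 1.74 and the difference 4.0 points.

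**2. Equal true risk in both arms.** The documents give no discontinuation percentages or AE timing, so these inputs are assumptions: 10% risk over a 210-day completer window (182 + 28 days), constant hazard, stopping independent of the event, and all early stops at Day 28 or all at Day 56.

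- Hazard h = -ln(0.90)/210 = 0.000502 per day.
- Risk if stopped at Day 28 (56-day window): 1 - exp(-56h) = 2.77%. At Day 56 (84-day window): 4.13%.
- Crude risk = (1 - p) × 10% + p × (risk in the short window), where p is the proportion stopping.
- Example, 20% versus 10% stopping at Day 28: mannitol 0.8 × 10 + 0.2 × 2.77 = 8.55%; control 0.9 × 10 + 0.1 × 2.77 = 9.28%. The ratio is 0.92 and the difference -0.7 points.

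| Stopping, mannitol v control | Crude ratio (true 1.00) | Difference, points |
|---|---|---|
| 15% v 8% | 0.95 to 0.96 | -0.5 to -0.4 |
| 20% v 10% | 0.92 to 0.94 | -0.7 to -0.6 |
| 30% v 15% | 0.88 to 0.90 | -1.1 to -0.9 |

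Because AE reporting ends 7 days after the last visit, a completer's nominal window is nearer 189 days (27 weeks). With 189 in place of 210 the ratios are 0.95 to 0.96, 0.93 to 0.94 and 0.88 to 0.91, so that choice matters little.

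**3. Unequal true risk, using the earlier hemoptysis figures as an illustration.** Assume 9.4% and 5.4% are the full 27-week risks, constant hazard, and 10% stopping on control. Each range runs from stops spread over weeks 0-6 to stops spread over 26 weeks.

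| Stopping on mannitol | Crude ratio (true 1.74) |
|---|---|
| 10% | 1.74 |
| 15% | 1.67 to 1.71 |
| 20% | 1.60 to 1.68 |
| 30% | 1.47 to 1.61 |

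At 20% the loss is about 4 to 8% of the ratio (1.68/1.74 = 0.96 or slightly above; 1.60/1.74 = 0.92), and the difference shrinks from 4.0 to between 3.0 and 3.5 points. An extreme gap of 5% on control versus 30% on mannitol, all within six weeks, gives 1.41.

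**4. Early events.** If half the hazard falls in the first 4 weeks, the 20% mannitol row in step 3 becomes 1.67 to 1.70. Returning to the 10% equal-risk case at 20% versus 10% stopping, with half the hazard in the first 28 days, the crude ratio is 0.96 to 0.97 and the person-time rate ratio is 1.03 to 1.04. The rate then errs by a similar amount in the other direction.

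**5. Precision.** With 423 randomized (SAP 10), about 211.5 per arm, and an assumed 10% in each arm, the 95% half-width for a risk difference is 1.96 × sqrt(2 × 0.1 × 0.9/211.5) = 5.7 points. That exceeds the 4.0-point difference in the earlier trials.

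**The case against.** A reader might infer that the plan does understate mannitol's risks. The documents do not support that. They give no stopping percentages for this trial. The drop-out remark concerns the earlier trials and appears in a discussion of imputation after trial withdrawal, whereas the AE window depends on stopping drug, which SAP 7.1.2 and 7.1.3 treat separately. With equal stopping there is no relative bias.

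A reader might also take 9.4% versus 5.4% as an adult signal. Those figures come from trials that enrolled from age six (Protocol 1.1.4), and the adult post-hoc comparison was described as similar.

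Other points that stand:
- The distortion is small beside a half-width of 5.7 points.
- An event that causes the stop is already counted, early events reduce the loss, and under a nominal 27-week window a subject stopping after about Week 23 loses nothing (27 - 4 = 23).
- Exposure is summarized (SAP 9.1), time to stopping drug gets a Kaplan-Meier analysis (7.1.3), and fatal AEs, serious AEs and AEs leading to withdrawal are listed (9.3). A reader could see an imbalance, though could not rebuild rates by preferred term.
- Counting each subject once per SOC and PT is standard, and person-years for a recurrent efficacy endpoint do not oblige the same for AEs.
- Person-time rates have their own bias, as step 4 shows, so they should not simply replace percentages.
- The form of the hemoptysis summary is unstated and the appendices are redacted, so a time-adjusted table cannot be ruled out.

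None of this removes the case for stating a time-at-risk estimate in advance. The size of any stopping gap was unknown when the SAP was finalized before unblinding, and choosing the estimate after seeing the gap would be weaker.

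**Conclusion.** The point holds in conditional form. The readable SAP reports TEAEs, including hemoptysis, without adjustment for time at risk, in a window tied to the last dose. If more subjects stop drug early on mannitol, crude percentages may modestly understate its relative risk: about 4 to 8% on the ratio at 20% versus 10% stopping, with absolute shifts of 0.4 to 1.1 points across the equal-risk scenarios.

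These sizes rest on assumed stopping proportions, constant hazard and stopping unrelated to the event. They fall to zero on the ratio scale if stopping is equal, shrink if events come early or cause the stop, and grow only with a wide early gap. The gain is less in correcting a large error than in giving the prospective adult hemoptysis comparison an estimate with time at risk and uncertainty attached.

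**What to change.** Keep the crude tables, and add to SAP 9.3:

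- **Hemoptysis:** Kaplan-Meier cumulative incidence of the first event from first dose over the on-treatment window, with the between-arm difference at a stated day and its 95% CI. No hypothesis test is needed, so this is compatible with SAP 9.
- **Hemoptysis, all TEAEs, serious TEAEs and related TEAEs:** first-event rates per 100 person-years in the same window, with person-time ending at the first event. Show these as supplementary columns, not as the sole basis for the between-arm statement.
- **Assumptions to state:** the rates assume a constant hazard, and censoring at last dose plus 28 days assumes non-informative stopping.

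The cost is a few extra tables and one curve from dates already collected. If the redacted appendices already specify this, a cross-reference in 9.3 is enough.

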## Statistical Analysis Plan

PT. Tables will be sorted by decreasing frequency (overall) of SOC, and then, within a SOC, descending frequency (overall) of PT.

Trial medication related AEs are defined as those that are ‘possibly related’, ‘probably related’, or ‘definitely related’. Relationship to trial medication is not expected to be missing after data cleaning, however, if relationship is confirmed as missing, the AE will be considered as related.

An overall summary table of TEAEs will be presented detailing the number and percentage of subjects, and number of events for the following categories:

- At least one TEAE.
- TEAEs related to trial medication.
- Serious TEAEs.
- Related serious TEAEs.
- TEAEs leading to permanent discontinuation of trial medication.
- TEAEs leading to withdrawal from the trial.
- TEAEs leading to death.

[figure not shown]
The incidence of all TEAE by SOC and PT will be presented for the following:

- All TEAEs.
- TEAEs related to trial medication.
- Serious TEAEs.
- Related serious TEAEs.
- TEAEs leading to permanent discontinuation of trial medication.
- TEAEs leading to withdrawal from the trial.

In addition, a summary of all TEAEs by maximum intensity (mild, moderate, severe), SOC, and PT will be presented, where the maximum intensity per subject will be counted at each level of summarization. AEs leading to death (all AEs with outcome recorded as ‘Fatal’ on the CRF), serious AEs (all AEs marked as serious on the CRF), and AEs Leading to withdrawal from the trial (all AEs with ‘Did the subject withdraw from the study due to this event?’ recorded as ‘Yes’ on the CRF) will be listed separately.

MEAEs will be summarized by SOC and PT for the MTT set.

[figure not shown]
Additional information has been collected for AEs that are considered to be hemoptysis events in this trial i.e. information on infection, hemoptysis volume, and whether the hemoptysis occurred concurrently with an exacerbation. These data will be listed and summarized separately.

Pharmaxis Ltd

DPM-CF-303

Final v1.0

## Statistical Analysis Plan

### 9.4. VITAL SIGNS

Vital signs assessment and absolute change from baseline in SBP (mmHg), DBP (mmHg), heart rate (beats/min), respiratory rate (breaths/minute), SpO2 (%), temperature (°C) and weight (kg) will be summarized by visit using summary statistics for continuous variables.

### 9.5. PHYSICAL EXAMINATION

Physical examination data (decrease in breath sounds/wheezing, crackles, retraction, and clinically significant findings) will be summarized by visit using summary statistics for categorical variables.

## Statistical Analysis Plan

### 10. SAMPLE SIZE RE-ESTIMATION

A formal sample size re-estimation was planned to be performed after at least 300 subjects have been recruited and at least 100 subjects had Visit 4 (Week 26) spirometry data available.

This blinded sample size re-estimation was based on the methods of Kieser and Friede which preserve the overall Type 1 error rate. Thus no adjustments to the overall significance level for the trial are required.

Further details are provided in a separate sample size re-estimation plan (final Version 1.0, dated 07Dec2015).

The outcome of the sample size re-estimation was to increase the sample size required to 440 subjects. In total, 423 subjects were randomized.

## Statistical Analysis Plan

### 11. CHANGE FROM ANALYSIS PLANNED IN PROTOCOL

1. The analysis of spirometry endpoints has been updated to report relevant endpoints using L, as recorded in the CRF, rather than mL, as specified in the protocol, to keep consistency between data collection and final reporting.
2. The 4 hierarchical secondary endpoints and one non-hierarchical secondary endpoint listed below have been clarified to refer to PDPEs rather than PEs. All analyses will be repeated for PEs (defined as all events recorded on the PE Review CRF page that have associated antibiotic use) however the hierarchical testing will be based on the PDPE endpoints (Section 4.2):
  - Time to first PDPE.
  - Number of days on antibiotics (oral, inhaled, or IV) due to PDPE.
  - Number of days in hospital (admissions only) due to PDPE.
  - Rate of PDPE (per person year) over the 26-week treatment period.
  - Incidence of PDPEs over the 26-week treatment period.
3. The criteria to determine if a subject will be included in the PP set were adjusted during the BDRM and local major deviations were defined for the visit if the spirometry assessment was determined to be non valid, leading to the exclusion of all the specific assessment's data collected at the visit from the PP analysis. All the decisions made are documented in the [REDACTED] which will be finalized prior to unblinding the trial.
4. Time to event derivations will be based on date of randomization (Trial Day 1) for all subjects rather than date of first treatment (Treatment Day 1), except for time to discontinuation from trial medication, to allow consistency of derivations between randomized and treated and randomized but non-treated subjects.
5. Baseline FEV1 has been added as a continuous, fixed covariate in the REML based MMRM model, or the appropriate baseline value of the analysis variable (i.e. baseline percent predicted FEV1, baseline FVC, baseline VAS score, or baseline CFQ-R respiratory domain score).
6. For IUDR, BOCF imputations will be done for AE, death, physician decision, and lack of efficacy, while not for lost to follow-up; the logic behind this choice is the fact that motivation for the latter is not related to safety.
7. The BOCF imputation based on IUDR methodology will not be applied to all the missing post-baseline FEV1 measurements, but only to those which are missing as a result of withdrawal from the trial (i.e. missing intermediate FEV1 will not be

## Statistical Analysis Plan

imputed). It is assumed that a MAR missingness pattern is the most probable in this context.

8. Protocolled primary sensitivity analyses #1 remains unchanged but has become primary sensitivity analysis #3. It will be performed to elicit insights into the effect of imputation via the planned BOCF+IUDR framework and the primary analyses will be repeated without imputation of missing post-baseline FEV1.
9. Protocolled primary sensitivity analyses #2, #3, #5, #7, and #9 have been removed to provide a more targeted and focused set of analyses to test the robustness of the primary results to varying assumptions (Section 8.1).
  - a. Protocolled primary sensitivity analysis #2 was to elicit insights into the effects of including data from subjects after cessation of trial treatment and the primary analyses was to be repeated excluding these data both with imputation of missing post-baseline FEV1 assessments and without imputation. These analyses will now be included as supportive analyses (Supportive analyses 6 and 8).
  - b. Protocolled primary sensitivity analysis #3 was sensitivity of the primary result to choice of “across Weeks 6 to 26” versus “at Week 26” estimates of the treatment effect, gauged by computing the LS mean treatment group difference at Week 26; this result will be presented as part of the primary endpoint primary analysis and is now included as a supportive analysis (Supportive analysis 2).
  - c. Protocolled primary sensitivity analysis #5 was to determine if the primary results are sensitive to any observed changes between screening and Visit 1 in FEV1, and the primary analysis was to be repeated using the mean FEV1 measurement from screening (Visit 0) and Visit 1.
  - d. Protocolled primary sensitivity analysis #7 was a responder analysis where the cut-off for classification as a responder was to be change from baseline FEV1 greater than: -300, -250, -200, -150, -100, -50, 0, 50, 100, 150, 200, 250, and 300 mL respectively.
  - e. Protocolled primary sensitivity analysis #9 was to explore the effect of different imputation methods, the primary analysis was to be repeated using a worst observation carried forward+IUDR method rather than the BOCF+IUDR framework.
10. Primary sensitivity analysis #4 has become primary sensitivity analysis #1 and has been changed to use the Ratitch method (Section 8.1.2). The intention of this

